8.2. Setting

[figure not shown]
This study will be conducted using data from four Nordic countries: Denmark, Finland, Norway, and Sweden (listed alphabetically) in each country, all live births and stillbirths are recorded in the birth registries (in all countries from gestational week 22 from July 2008 onwards; in Sweden, from gestational week 28 until July 2008). During those periods there were approximately 580,000 – 730,000 live births in each of Denmark, Finland, and Norway, and 800,000 in Sweden.¹⁶ The start of the study period in each country is selected to ensure availability of pregabalin and the candidate comparator on the market and availability of data on outpatient dispensings for at least 12 months before the end of the earliest identified pregnancy. For example, pregnancy ending at term with a live birth on 1 January 2005 in Denmark will have prescription history from 1 January 2004, thus covering the 9 months of gestation and 3 months preconception.

Population-based healthcare registries in Nordic countries are an optimal setting for examining safety of medicines in pregnancy. Their most important strengths are capture of all births and, in some cases, clinically relevant birth and postnatal outcomes; routine capture of dispensings of prescription medications to pregnant women; extensive information about maternal and offspring health outcomes; and exact linkage between the maternal and the offspring record. Thus, unlike studies based e.g., on data from TIS, there is no risk of bias by self-referral, recall, or access to health care. Dispensings of medicines represent a better proxy of actual drug intake than do issued prescriptions (primary compliance), reducing misclassification of the actual drug intake.

Study population

The study population consists of all pregnancies identified in the respective administrative registries from 1 January 2005 to 31 December 2015 in Denmark, Finland, and Norway and all pregnancies identified from 1 July 2006 to 31 December 2013 in Sweden, Figure 1 .

Figure 1. Study population flow diagram

All singleton and multiple gestations ending in live birth or stillbirth will be identified in each country's birth registry from 1 January 2005 to 31 December 2015 in Denmark, Finland, and Norway and pregnancies identified from 1 July 2006 to 31 December 2013 in Sweden. As all birth outcomes will have occurred as of the date of delivery, prevalence will be used as a measure of outcome occurrence.¹⁴ However, to allow for delayed reporting/diagnosis, all congenital malformations diagnosis recorded until one year of age will be included, according to the standard procedure used by the European Network of Congenital Anomaly Registers (EUROCAT)¹⁷ through the end of 2016 in Denmark, Finland and Norway and through the end of 2014 in Sweden. In addition, available information on pregnancies ending in 2nd trimester therapeutic induced abortions will be identified in Denmark, Finland and Norway.¹⁸ Information on pregnancies ending in 2nd trimester therapeutic induced abortions is not available from Sweden. It will be especially important to identify pregnancy terminations due to malformations of the nervous system, as nearly half of the pregnancies affected by nervous system malformations may be terminated.¹⁸

For the birth outcomes, stillbirth prevalences at birth will be described and compared among the live and still born infants. For the birth outcomes other than congenital malformations or stillbirth, prevalences at birth will be described and compared.

For the postnatal neurodevelopmental outcomes, live-born offspring of all pregabalin-exposed and the comparator pregnancies will be followed from the date of birth until the earliest record of a given outcome of interest, emigration (except Sweden and Norway, where emigration data are unavailable), death, or end of study (31 December 2014 in Sweden; 31 December 2016 in the other countries); for this analysis children in Norway born before 2008 will be excluded as the Patient Registry of Norway was launched in 2008. Thus, for the neurodevelopmental postnatal outcomes, live-born children will be followed up to a minimum of 1 year and a maximum of 10 years postnatally in Denmark, Finland, and Norway and up to a maximum 8.5 years postnatally in Sweden (Figure 2).

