8.2.1. Inclusion criteria

All pregnancies identified from 1 January 2005 through 31 December 2015 (both dates inclusive) in Denmark, Finland, and Norway and all pregnancies identified from 1 July 2006 through 31 December 2013 (both dates inclusive) in Sweden.

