8.3.2. Outcomes

This study will describe use and assess safety of pregabalin use during pregnancy based on a series or birth and postnatal outcomes. For each outcome defined below, the population (denominator), period of pregnancy identification, and follow-up for outcome assessment are described in Table 2.

Table 2. Types of pregnancies included in analysis of each outcome for the primary analyses, secondary analyses, and sensitivity analyses

Outcome	Study population and period of pregnancy identification				Follow-up for outcome assessment
	Denmark	Finland	Norway	Sweden	

Table 2. Types of pregnancies included in analysis of each outcome for the primary analyses, secondary analyses, and sensitivity analyses

Outcome	Study population and period of pregnancy identification				Follow-up for outcome assessment
	Denmark	Finland	Norway	Sweden	
Primary analyses	Major congenital malformations (overall and specific)	Pregnancies ending in singleton/multiple live birth, stillbirth, 1Jan2005 - 31Dec2015 inclusive		Pregnancies ending in singleton/multiple live birth or stillbirth 1Jul2006-31Dec2013 inclusive	Prevalence at birth with outcomes identified at birth, and until the first birthday (inclusive) through 2016 in Denmark, Finland and Norway and through 2014 in Sweden
	Stillbirth	Pregnancies ending in singleton/multiple live birth, stillbirth, 1Jan2005 - 31Dec2015 inclusive		Pregnancies ending in singleton/multiple live birth or stillbirth 1Jul2006-31Dec2013 inclusive	Prevalence at birth
	Low birth weight	Pregnancies ending in singleton/multiple live birth, 1Jan2005 - 31Dec2015 inclusive		Pregnancies ending in singleton/multiple live birth 1Jul2006-31Dec2013 inclusive	Prevalence at birth
	SGA ¹⁹				
	Preterm birth				
Secondary analyses	Low Apgar score at 5 minutes				
	Microcephaly				
	Attention deficit hyperactivity disorder	Pregnancies ending in singleton/multiple live birth, 1Jan2005 - 31Dec2015 inclusive	Pregnancies ending in singleton/multiple live birth, 1Jan2008 - 31Dec2015 inclusive	Pregnancies ending in singleton/multiple live birth 1Jul2006-31Dec2013 inclusive	Minimum 1 year postnatally. Maximum available postnatally, 31Dec 2016 Denmark, Finland, Norway; 31Dec 2014 Sweden.
Sensitivity analyses	Autism spectrum disorders				
Sensitivity analyses	Learning disabilities (including mental retardation)				

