8.3.2.1. Primary Outcomes (Birth outcomes)

- Major congenital malformations, any and specific, according to the European Network of Congenital Anomaly Registers (EUROCAT) classification²⁰
- Stillbirth, as recorded in each country's birth registry
- Low birth weight (birth weight < 2500 g)
- Small for gestational age (SGA), defined, for singleton pregnancies, as a dichotomous variable (yes/no) of birth weight below 2 standard deviations (SDs) of sex- and gestational week specific distributions, using country-specific reference standard.^{19,21} SGA non-singleton gestations will be defined if appropriate reference standard can be defined/identified; otherwise set to missing.
- Preterm birth, defined as gestational age <37 weeks
- Low Apgar score at 5 minutes, defined as a dichotomous variable (score 0-6 vs. score 7-10)
- Microcephaly, defined as a dichotomous variable (yes/no) of head circumference at birth (cm) smaller than 2 SD of sex- and gestational week specific distribution, using country-specific reference standard

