8.5. Study size

Table 4 shows estimated number of total pregnancies ending in live or stillbirth and pregnancies with exposures and indications potentially relevant for analysis.

Table 4. Estimated numbers of pregnancies ending in live or still birth for potentially analysis-relevant categories

	Denmark (2005-2016)	Finland (2005-2014)	Norway* (2005-2016)	Sweden (2006-2013)
Pregnancies ending in live/still birth	730,000	580,000	650,000	800,000
Pregnancies with dispensation of				
Pregabalin, first trimester	200	700	200	400
Pregabalin, any time during pregnancy	350	900	350	800
Lamotrigine, first trimester	2000	900	2000	1300
Lamotrigine, any time during pregnancy	2700	1100	2700	1800
Duloxetine, first trimester	400	500	400	500
Duloxetine, any time during pregnancy	800	600	800	1000

*Pilot data not available; estimated based on pilot data from Denmark due to similar s population size.

The estimated numbers of pregnancies ending in live or still birth for potentially analysis-relevant categories for Norway were unavailable at the time of the protocol writing but are estimated in Table 4 by imputing data from Denmark, where the number of pregabalin users was the lowest, to provide the most conservative estimate. Based on this and on each country’s population size, conservatively estimated achievable size for this study will be more than 1000 pregnancies exposed to pregabalin during the first trimester.^{20,51} Table 5 shows the maximum upper limit of the 95% confidence interval of risk ratio that can be ruled out with 80% probability, for different scenarios with respect to the size of the exposed and comparator groups conservatively assuming N=1000 to be the size of pregabalin-exposed pregnancies. This analysis assumes that the true underlying risk ratio is 1.0 (no association between pregabalin exposure and an endpoint). For example, assuming the background prevalence of major congenital malformations to be 3%, underlying pregabalin-associated RR, and allocation ratio of comparator to pregabalin of 119:1 (corresponding to pregabalin exposure prevalence 0.8%), the analysis will rule out a RR with an upper confidence limit of 1.65845.

Table 5. Maximum upper limits of 95% confidence interval for risk or prevalence ratios depending on the prevalence of selected outcomes representative of prevalence of various study outcomes

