8.7.1. Calculation of prevalences of birth outcomes

Prevalence of each birth outcome will be computed as number of newborns with a given outcome divided by the total number of newborns at risk. For the outcomes of congenital malformations and stillbirth in the analysis not including pregnancies ending in 2nd trimester abortion the number of newborns at risk will be the total number of live or stillborn children. For the outcomes of congenital malformations and stillbirth in the analysis including pregnancies ending in a 2nd trimester abortion the number of newborns at risk will be the number of live or stillborn children and the number of pregnancies ending in a 2nd trimester abortion. For the other birth outcome the number of newborns at risk will be the number of liveborn newborns.

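### Stillbirth has no gestational threshold of its own, and Sweden's recording rule moves from week 28 to week 22 inside the study window, so Swedish stillbirth figures mix two definitions

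*Protocol*

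**What the plan says.** Section 8.3.2.1 lists the outcome as "Stillbirth, as recorded in each country's birth registry". The other birth outcomes in that list have their own cut-offs (2500 g, 37 weeks, Apgar 0–6, 2 SD), or, for malformations, a named classification. Stillbirth has neither.

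Section 8.2 describes registration of live births and stillbirths as "in all countries from gestational week 22 from July 2008 onwards; in Sweden, from gestational week 28 until July 2008". The Swedish inclusion criterion in 8.2.1 is "all pregnancies identified from 1 July 2006 through 31 December 2013 (both dates inclusive) in Sweden", and the stillbirth row of Table 2 repeats that window: "Pregnancies ending in singleton/multiple live birth or stillbirth 1Jul2006-31Dec2013 inclusive". The Swedish data therefore span the change.

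For stillbirth, 8.7.1 says that "the number of newborns at risk will be the total number of live or stillborn children". Sections 8.2, 8.7.1, 8.7.4 and 8.7.4.1, which describe the stillbirth analysis, contain no common threshold, no restriction and no split at July 2008. The limitations in 8.9 do not mention the change.

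Three other provisions bear on the point. Calendar year of delivery is among the covariates for the propensity score (8.3.3). Crude as well as adjusted ratios are reported and pooled (8.7.3.1, 8.7.7). Section 8.2 also handles another registry discontinuity by restriction: Norwegian children born before 2008 are left out of the neurodevelopmental analysis because the patient registry started that year.

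**The concern.** Until July 2008, a Swedish foetal death at weeks 22–27 is not in the birth register. It is neither a case nor part of the denominator. After that date it is both. One primary outcome therefore has two meanings within one country, and that country is the largest by pregnancies ("approximately 580,000 – 730,000 live births in each of Denmark, Finland, and Norway, and 800,000 in Sweden").

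Two things are at stake. The first is the descriptive objective: a Swedish stillbirth prevalence that averages two definitions is not directly comparable with the other three countries. The second is the crude ratio. If the exposed and unexposed groups are spread differently over calendar time, the definition change enters the ratio as an artefact.

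Section 8.7.7 justifies fixed-effect pooling partly by well-defined outcomes across countries, and stillbirth does not yet meet that premise. The heterogeneity check there compares countries, so it would not reveal a change within Sweden.

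**Working it through.** **Inputs from the protocol**
- Swedish window: 1 July 2006 to 31 December 2013 (8.2.1). Threshold change: July 2008 (8.2), taken here as 1 July.
- Stillbirth prevalence: 0.6% (Table 5). No threshold is attached to this figure; it is treated here as the week-22+ prevalence.
- Pregnancies exposed to pregabalin at any time, the exposure used for stillbirth (Table 4): Denmark 350, Finland 900, Norway 350, Sweden 800; total 2400.
- Table 5 settings: two-sided 95% interval, 80% probability, true ratio 1, 1000 exposed, 119:1.

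**Inputs assumed, because the protocol does not give them**
- *f*, the share of week-22+ stillbirths that occur at weeks 22–27: 20–50%.
- *e*, the share of Swedish exposed deliveries before July 2008: 5% up to 26.7% (the last equals the unexposed share).
- The other three countries recorded from week 22 throughout. Section 8.2 names only Sweden as the exception.

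**1. Reproduce the plan's figure.** Upper limit = exp[(1.960 + 0.842) × √{(1−p)/(p·n) × (1 + 1/119)}]. With p = 0.006 and n = 1000 this gives 3.14, against 3.1 in Table 5. The stillbirth precision figure reproduces.

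**2. Share of the Swedish window under the week-28 rule.** w = 731/2741 = 26.7%. With even birth rates, that is 0.267 × 800,000 ≈ 213,000 Swedish pregnancies, or 7.7% of the 2,760,000 in Table 4.

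**3. Swedish prevalence.** 0.60% × (1 − w·f):
- f = 20%: 0.60 × (1 − 0.0533) = 0.57%
- f = 50%: 0.60 × (1 − 0.1333) = 0.52%

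**4. Swedish crude ratio against the unexposed when the true ratio is 1.** (1 − e·f)/(1 − w·f), with the unexposed spread evenly over the window:

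| f | e = 5% | e = 10% | e = 15% | e = 26.7% |
|---|---|---|---|---|
| 25% | 1.06 | 1.04 | 1.03 | 1.00 |
| 40% | 1.10 | 1.07 | 1.05 | 1.00 |
| 50% | 1.13 | 1.10 | 1.07 | 1.00 |

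**5. Pooled crude ratio.** Sweden holds 800/2400 = one third of the exposed. With roughly that weight on the log scale, 1.03^(1/3) ≈ 1.01 and 1.13^(1/3) ≈ 1.04.

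**6. Adjusted ratio.** Year of delivery in the propensity score aligns the comparator with the exposed year by year, so only the split within 2008 can remain. Illustration (assumed): 10% of exposed deliveries in 2008, 40% of those before July against 50% in the weighted comparator, f = 50%. The numerator differs by 0.10 × 0.10 × 0.50 = 0.005. Divided by at least 0.867, this is a ratio below 1.01.

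**7. Precision after restriction.** Leaving out Swedish deliveries before July 2008 removes 0.267 × 800 ≈ 213 of 2400 exposed (8.9%) if use is even over time. By the formula in step 1, the limit moves from 2.09 (n = 2400) to 2.17 (n = 2187).

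**8. Precision at week 28+ everywhere.** Prevalence falls to 0.48% (f = 20%) or 0.30% (f = 50%). With n = 2400 the limit is 2.29 or 2.85.

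**The case against.** The strongest reply is that little of this reaches the estimates that matter. Calendar year is specified for the propensity score, balance is checked in each country, and by step 6 the residue in the adjusted ratio is negligible under plausible inputs. That stands. It leaves the crude prevalences and crude ratios, which the plan reports, and the crude ratios are also pooled.

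The size is also small against the noise. Sweden expects 800 × 0.6% = 4.8 exposed stillbirths, so its 95% interval spans a factor of about 2.4 each way. That stands too, but it does not excuse an undefined primary outcome.

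A reader might infer that the crude ratio is biased upward. The protocol gives no calendar distribution of Swedish exposure. Section 8.9 says, about the neurodevelopmental outcomes, that exposed numbers in the earlier period may be too few. This makes lower early use plausible but does not establish it for Sweden. With equal distributions the ratio is exactly 1.00. The calculation also covers only the unexposed comparator, not lamotrigine or duloxetine.

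A reader might also infer that the Swedish prevalence cannot be interpreted, or that pooling different thresholds is itself a bias. Neither follows. The dilution is mild and 8.2 discloses its cause. Ratios are formed within each country, and different baseline prevalences do not bias a common ratio.

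Finally, Annex 3 holds the operational definitions and is not shown, so a threshold there cannot be excluded. The main text nevertheless defines the outcome as whatever the registry recorded.

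**Conclusion.** The point holds as a defect of definition. A primary outcome is left without a threshold although the protocol itself reports that Sweden's recording rule changes part-way through the Swedish window. About 27% of that window uses the narrower rule.

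The dilution of the Swedish prevalence in step 3 follows for any f above zero. The shift in the crude ratio in step 4 is conditional on lower pregabalin use before July 2008. It is smaller still in the pooled crude ratio, and mostly removed from adjusted ratios. Both f and e are assumptions; the day count and exposed counts come from the protocol.

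Two limits on scope. Sweden is the largest country by pregnancies but not by exposure, where Finland has 900 against 800. Table 5's stillbirth row reproduces, so this is not a sample-size error. The live-plus-stillbirth population for major malformations shifts in the same way, but more weakly.

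**What to change.** In 8.3.2.1 and the stillbirth row of Table 2, set one threshold: stillbirth at 22 weeks or later, with Swedish deliveries before the July 2008 change left out of the stillbirth analysis only. State the exact date of the change.

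Add a sensitivity analysis of stillbirth at 28 weeks or later in all four countries and all years, using the gestational age held in the birth registers (Table 3). Mention the change in 8.9.

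Setting 28 weeks in Sweden alone would not serve, because the pooled estimate would still mix thresholds.

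The cost is about 27% of Swedish deliveries for this one outcome, with the small loss of precision in step 7. The restricted Swedish set is a separate study population under 8.7.3.1, so its any-trimester propensity scores need re-estimating. The week-28 analysis is less precise (step 8), which is a reason to keep it as the sensitivity analysis.

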Sensitivity analyses	Major congenital malformations (overall and specific) including malformations identified prenatally	Pregnancies ending in singleton/multiple live birth, stillbirth, 1Jan2005 - 31Dec2015 inclusive and pregnancies ending in therapeutic 2 nd trimester induced abortion, 1Jan2005-31Dec2015 inclusive (Denmark, Norway) 31Dec2012 (Finland)		None	Prevalence at birth with outcomes identified prenatally, at birth, and until the first birthday (inclusive) through 2016 in Denmark and Norway and 31Dec2016 in Finland

SGA, Small for gestational age.

* The Patient Registry of Norway, the source of data for the postnatal outcomes, has existed from 2008.

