8.3.3. Covariates and other population characteristic

Characteristics of the study population will include perinatal covariates and covariates of the mother. Perinatal covariates include calendar year of delivery, maternal age at conception, parity (number of live and still births prior to the on-study pregnancy); marital/cohabiting status; pregravid body mass index (BMI) as recorded at the first antenatal visit or via a hospital diagnosis of obesity; smoking during pregnancy as recorded at the first antenatal visit; single or multiple gestation; Caesarean delivery; and child's sex. Caesarean delivery and child's sex will be reported but will not be used for adjustment. Indication for pregabalin use in 12-months pre-LMP (epilepsy, neuropathic pain, GAD and related disorders) will be reported descriptively but will not be used for adjustment.

[figure not shown]
Covariates of the mother considered for adjustment (inclusion in propensity-score model) will include:

- calendar year of delivery;
- age in years at conception;
- marital/cohabiting status;
- smoking during pregnancy;
- Obesity (BMI ≥ 30 kg/m²) or a hospital diagnosis of obesity;
- Single or multiple gestation
- hospital-recorded morbidity based on inpatient and outpatient specialist care or proxy medication use in 12 months pre-LMP: migraine or other headache syndromes, other neurologic disorders, depression, bipolar disorder, alcohol abuse or dependence, drug abuse or dependence, hypertension, haematological diseases, diabetes, asthma, liver diseases, renal impairment, rheumatic diseases, obesity, disorders of female pelvic organs/genital tract, thyroid disorders, infections [infections will be assessed in 90 days pre-LMP]. In Finland, in addition to the hospital diagnoses, diagnoses from primary care are also available and will be used;
- indicators of maternal health care utilisation in the 12 months pre-LMP (number of inpatient and specialised outpatient encounters);
- for the outcome congenital malformations: maternal medication use each as a dichotomous variable, defined by at least one dispensing during the first trimester (AEDs, antidepressants, hypnotics, antipsychotics, analgesics, antihypertensives, non-steroidal anti-inflammatory drugs, drugs for peptic ulcer/gastroesophageal reflux, folic acid, drugs for in-vitro fertilization, thyroid hormones, systemic corticosteroids, and antiinfectives for systemic use);

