	Pregnancies ending in therapeutic 2nd trimester induced abortion	Finnish Register on Induced Abortions* Norwegian Register of Pregnancy Terminations (part of the Medical Birth Registry of Norway) Not available in Sweden	ICD-10

Table 3. National registries in Denmark, Finland, Norway and Sweden and type of data available from each registry

Study variable/role	Type of data	Data source(s)	Coding system(s) used
Exposure (for full list see Section 8.3.1)	Maternal dispensings of pregabalin, lamotrigine, duloxetine	Danish National Health Services Prescription Database ^{45,46} Finnish Prescription Register ⁴⁵ Norwegian Prescription Database ⁴⁵ Swedish Prescribed Drug Register ⁴⁵	ATC
		Outcome (for full list see Section 8.3.2)	Major congenital malformations
Birth weight, gestational age, Apgar score at 5 minutes, head circumference, stillbirth	Danish Medical Birth Registry Finnish Medical Birth Register* Medical Birth Registry of Norway Swedish Medical Birth Register	A specific variable in each birth registry	
Neurodevelopmental outcomes	Danish National Patient Registry ⁴³ Danish Psychiatric Central Research Register ⁴⁷ Danish Psychiatric Central Register Finnish Care Register for Health Care Finnish Register of Primary Health Care visits Norwegian Patient Registry ^{48±} Swedish National Patient Register ^{29,49} Danish National Health Services Prescription Database ^{45,46} Finnish Prescription Register ⁴⁵ Norwegian Prescription Database ⁴⁵ Swedish Prescribed Drug Register ⁴⁵	ICD-10 for diagnoses, ATC codes for drug proxies	
Characteristic of study population and covariates (for full list see Section 8.3.3)	Mother: age, parity, marital/cohabiting status, mode of delivery, smoking during pregnancy, BMI	Danish Medical Birth Registry Finnish Medical Birth Register* National Registry of Norway ⁵⁰ Swedish Medical Birth Register ⁴²	A specific variable in each birth registry
	Offspring: sex, multiplicity of gestation		

Table 3. National registries in Denmark, Finland, Norway and Sweden and type of data available from each registry

Study variable/role	Type of data	Data source(s)	Coding system(s) used
Maternal morbidity (including indication for pregabalin) Markers of health care utilisation		Danish National Patient Registry, ⁴³ Finnish Care Register for Health Care Finnish Register of Primary Health Care visits Norwegian Patient Registry ⁴⁸ Swedish National Patient Register ^{29,49}	ICD-10 for diagnoses, ATC for medication proxies

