		Danish National Health Services Prescription Database ^{45,46} Finnish Prescription Register ⁴⁵ Norwegian Prescription Database ⁴⁵ Swedish Prescribed Drug Register ⁴⁵	
Maternal medications		Danish National Health Services Prescription Database ^{45,46} Finnish Prescription Register ⁴⁵ Norwegian Prescription Database ⁴⁵ Swedish Prescribed Drug Register ⁴⁵	ATC
Loss to follow-up		Danish Civil Danish Civil Registration System ⁴¹	A specific variable in each registry
Death, emigration [†]		Finnish Causes of Death Register Finnish Population Register Centre National Registry of Norway Swedish Cause of Death Register	

*Data for the Medical Birth Register, the Register on Induced Abortions, the Malformation Register and the Prescription Register (3 months before last menstrual period) can be obtained from the Finnish Drugs and Pregnancy Project (DPP) database.

[†]Emigration data not available in the Swedish or the Norwegian dataset

[‡]Data available from 2008 onwards in Norway

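### Norwegian births from 2005 enter the adjusted analyses, but the registry behind their hospital-based covariates starts in 2008, so about 43% of the Norwegian birth window lacks the 12-month look-back

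*Protocol*

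**What the plan says.** **Birth window.** Section 8.2.1 includes "All pregnancies identified from 1 January 2005 through 31 December 2015 (both dates inclusive) in Denmark, Finland, and Norway". Table 2 gives the same window for the primary birth outcomes: "Pregnancies ending in singleton/multiple live birth, stillbirth, 1Jan2005 - 31Dec2015 inclusive". Norway has no later start for these analyses.

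**Covariates.** Section 8.3.3 lists, for the propensity score, a set of morbidities taken from inpatient or specialist outpatient care or from proxy medication in the 12 months before the LMP (infections: 90 days). It also lists "indicators of maternal health care utilisation in the 12 months pre-LMP (number of inpatient and specialised outpatient encounters"). Section 8.7.3.1 puts every prespecified covariate into every propensity score.

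**Source.** In Table 3 the row "Maternal morbidity (including indication for pregabalin) Markers of health care utilisation" names the Norwegian Patient Registry for diagnoses and the Norwegian Prescription Database for medication proxies. The table footnote on that registry reads "Data available from 2008 onwards in Norway".

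**Where the 2008 limit is applied.** Only to the children's postnatal outcomes: in section 8.2 ("for this analysis children in Norway born before 2008 will be excluded as the Patient Registry of Norway was launched in 2008") and in the footnote to Table 2 ("The Patient Registry of Norway, the source of data for the postnatal outcomes, has existed from 2008").

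**How the study start was chosen.** Section 8.2 rests it on the drugs being on the market and on "availability of data on outpatient dispensings for at least 12 months before the end of the earliest identified pregnancy". Availability of hospital diagnoses is not part of that reasoning.

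**The concern.** Three things the protocol fixes cannot all hold for Norway: births from 2005, a hospital source that starts in 2008, and a 12-month pre-LMP look-back in that source. The protocol noticed the registry start when it defined the children's outcomes but did not carry it over to the mothers' covariates.

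For the early Norwegian births, encounter counts and diagnosis-based morbidity cannot separate sicker from healthier mothers, so a result labelled adjusted is adjusted for less than section 8.3.3 promises. The balance check in section 8.7.3.1 (standardised mean difference below 0.1) compares recorded values only, so it cannot show imbalance in something that was never recorded. Norway's adjusted estimates are reported on their own as well as pooled, so a reader would take them to be adjusted in the same way as those of the other three countries.

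The distribution of indications, which is part of a primary objective, uses the same registry and look-back and has the same gap.

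**Working it through.** **Plan's own figure.** Section 8.5 states an upper limit of 1.65845 for any major malformation (3% prevalence, 1,000 exposed, ratio 119:1, true ratio 1.0, 80% probability). The formula exp[(z0.975 + z0.80) × sqrt((1 − p)/(p × n) × (1 + 1/119))] with p = 0.03 and n = 1000 gives exp(2.8016 × 0.18057) = 1.658. The figure reproduces and does not depend on this point. The formula is reused below.

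**Inputs**
- Norwegian birth window 1 January 2005 to 31 December 2015: 4,017 days (8.2.1, Table 2).
- Registry data from 2008, taken as 1 January 2008 (8.2, footnotes to Tables 2 and 3).
- Look-back of 12 months before the LMP (8.3.3).
- Table 4, Norway: 650,000 pregnancies and 200 with first-trimester pregabalin, imputed from Denmark. Four-country first-trimester pregabalin total: 200 + 700 + 200 + 400 = 1,500.
- Assumptions: 280-day gestation, with births and exposures spread evenly over the window.

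**Dates**
- LMP up to 1 January 2008: no look-back. Adding 280 days gives births up to about 7 October 2008, 1,375 days into the window: 1,375/4,017 = 34%.
- LMP before 1 January 2009: no look-back or a partial one. Adding 280 days gives births before about 8 October 2009, 1,741 days: 1,741/4,017 = 43%.
- The 43% therefore consists of 34% with no look-back and a further 9% with part of one.
- Gestations from 154 to 294 days give 31–35% and 40–44%. Table 4 labels Norway 2005–2016; with that longer denominator the shares are 31% and 40%.

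**Postnatal outcomes.** Births before 2008 are 1,095 days (27% of the full window), so the existing cut removes only part of the gap. Of the remaining 4,017 − 1,095 = 2,922 days, 1,741 − 1,095 = 646 days (22%) still lack a full look-back.

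**Counts on Table 4**
- Norwegian pregnancies: 650,000 × 0.342 = about 222,000 with no look-back; 650,000 × 0.433 = about 282,000 without a full one.
- First-trimester pregabalin in Norway: 200 × 0.342 = about 68 with none; 200 × 0.433 = about 87 without a full one.
- Share of pooled exposures: 68/1,500 = about 4.5%; 87/1,500 = 5.8%.
- Norway's share of all first-trimester exposures, all years: pregabalin 200/1,500 = 13%, lamotrigine 2,000/6,200 = 32%, duloxetine 400/1,800 = 22%.

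**Effect of restricting Norway.** Exposed: 1,500 − 87 = 1,413, still above the planned 1,000. At 3% prevalence and 119:1 the upper limit is 1.51 with n = 1,500 and 1.53 with n = 1,413.

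**Reach of the medication proxies.** In the section 8.2 example, a Danish birth on 1 January 2005 has dispensings from 1 January 2004. Its LMP is about 27 March 2004, so a 12-month look-back would need history from about 28 March 2003. If history starts on 1 January 2004, births to about 8 October 2005 (280/4,017 = 7% of the window) also fall short on proxies.

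**The case against.** The strongest reply is that much of the adjustment survives. Morbidity can be identified from proxy medication as well as from hospital care, and Norwegian dispensings do not depend on the Patient Registry. The propensity score also holds calendar year, age, marital status, smoking, BMI-based obesity, multiplicity and 13 medication classes, several of which carry the same morbidity signal. Calendar year limits mixing of early and late births within strata. Country results are shown separately, heterogeneity is examined, and section 8.9 admits residual confounding. Operational definitions sit in Annex 3, whose codes are not shown, and a SAP may say how unobservable covariates are coded.

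Most of this stands, and it rules out two stronger readings that a reader might infer. One is that every early Norwegian mother is coded as healthy: no coding rule is stated, and a woman with a proxy dispensing would still be flagged. The other is that confounding control fails in Norway: it is weakened for some covariates in some years, and births from about October 2009 have the full look-back. Indication is no part of the adjustment problem either, because section 8.3.3 keeps it out of the propensity score.

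What the reply does not remove: encounter counts have no substitute source; calendar year absorbs a difference between eras but cannot restore adjustment among the early births; section 8.9 names the missing Norwegian emigration data but not this gap; and no code list or SAP can supply records from before the registry existed.

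**Conclusion.** The point holds as an inconsistency within the protocol between birth window, data source and look-back. Hospital-based morbidity and utilisation covariates are unobservable for about 34% of the Norwegian 2005–2015 birth window, and about 43% lacks the full 12 months. The 2008 birth cut for postnatal outcomes leaves the same problem for births up to about October 2009.

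The effect on pooled results is limited: about 6% of first-trimester pregabalin exposures. The main effect is weaker adjustment in Norway's own estimates, and the planned balance check cannot detect it.

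These sizes assume 280-day gestation, an even spread of births and exposures, and Norwegian counts that Table 4 borrows from Denmark. If pregabalin use rose over the period, fewer than 87 exposed pregnancies are affected.

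**What to change.** In sections 8.2 and 8.7.3.1, choose one of two options before extraction:

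- **Restrict.** Limit Norway's propensity-score-adjusted analyses, for birth and postnatal outcomes alike, to pregnancies with LMP on or after 1 January 2009. Keep earlier Norwegian births for the crude prevalence and drug-use tables, but not for the indication table.
- **Separate score.** Keep the early births with their own propensity score that omits the registry-based covariates, and report the restricted analysis as a sensitivity analysis.

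Either way, state the gap in section 8.9. Shortening the look-back to a window common to all countries is no remedy, because Norwegian LMPs before 2008 would still have no hospital history.

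**Cost.** Protocol wording. Under restriction, about 43% of the Norwegian window leaves the adjusted analysis. On Table 4 that is about 87 of 1,500 pregabalin, 867 of 6,200 lamotrigine (2,000 × 0.433) and 173 of 1,800 duloxetine (400 × 0.433) first-trimester exposures. About 1,413 pregabalin exposures remain, and the upper limit at 3% prevalence against the unexposed moves from about 1.51 to 1.53. The second option keeps the numbers but adds a further propensity score per contrast in Norway.
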